3.6.2 Adverse events

General common rules for adverse events

All AEs will be coded to a LLT, PT, HLT, HLGT, and associated primary SOC using the Medical Dictionary for Regulatory Activities (MedDRA) version currently in effect at Sanofi at the time of database lock.

The AEs will be analyzed in the following 3 categories:

- Pre-treatment AEs: AEs that developed, worsened or became serious during the pre-treatment period.

- TEAEs: AEs that developed, worsened or became serious during the TE period
- Post-treatment AEs: AEs that developed, worsened or became serious during the post-treatment period

Similarly, the AE leading to deaths will be analyzed in the pre-treatment, TE and post-treatment periods.

The primary focus of AE reporting will be on TEAEs. Pre-treatment and post-treatment AEs will be described separately. Main summary will be per study period (Blinded Period, Open-Label Period) and overall.

If selected TEAEs from the Blinded Period can be clearly assigned to one of the study interventions treated lesions, they may be presented additionally assigned to the treatment of the corresponding lesion.

An AE with incomplete or missing date/time of onset (occurrence, worsening, or becoming serious) will be classified as a TEAE unless there is definitive information to determine it is a pre-treatment or a post-treatment AE.

If the assessment of the relationship to IMP is missing for an AE, this AE will be assumed as related to IMP. If the severity/grade is missing for an AE, the severity/grade will be left as missing. AEs which are possibly related to study intervention and have onset date after the first dose of SAR444727 will be considered possibly related to SAR444727, unless they are documented as possibly related to the study intervention formulation of the placebo-treated lesion and not possibly related to the study intervention formulation of the SAR4447272 Gel, 5%-treated lesion.

The AE tables will be sorted as indicated in [Table 3](#).

Table 3 - Sorting of AE tables

AE presentation	Sorting rules
SOC and PT	By the internationally agreed SOC order and decreasing frequency of PTs ^{a, b}
PT	By decreasing frequency of PTs ^a

^a Sorting will be based on the overall incidence

^b The table of all TEAEs presented by SOC and PT will define the presentation order for all other tables (eg, treatment-emergent SAE) presented by primary SOC and PT, unless otherwise specified.

Analysis of all adverse events

The overview of TEAEs with the details below will be generated:

- Any TEAE
- Any severe TEAE
- Any treatment emergent SAE
- TEAE leading to death, if any

- Any TEAE leading to permanent intervention discontinuation
- Any TEAE leading to permanent study discontinuation
- Any treatment emergent AE of special interest (AESI) (Expedited reports as described in section 8.3.7 of the protocol will be considered as AESIs)

The AE summaries of [Table 4](#) will be generated with number (%) of participants experiencing at least one event and sorted by the internationally agreed SOC order and decreasing frequency of PTs. Sorting will be based on experimental study drug intervention group (see [Table 3](#)).

Table 4 - Analyses of adverse events

Type of AE	MedDRA levels
All TEAE	Primary SOC and PT
TEAE related to IMP as per Investigator's judgment	Primary SOC, and PT
Treatment emergent SAE	Primary SOC, and PT
Treatment emergent SAE related to IMP as per Investigator's judgment [optional]	Primary SOC, and PT
TEAE leading to permanent intervention discontinuation [optional]	Primary SOC, and PT
TEAE leading to death (death as an outcome of the AE as reported by the Investigator in the AE page) [optional]	Primary SOC and PT
AESI	Primary SOC and PT

In addition, the all TEAE summary by Primary SOC and PT will be performed by trial impact (disruption) due to COVID-19 (coronavirus disease 19). The number (%) of participants experiencing at least one treatment emergent COVID-19 related AE by primary SOC and PT, if applicable.

Optional tables mentioned in [Table 4](#) are to be done in case of sufficient number of events.

Deaths, serious, and other significant adverse events

Deaths and SAEs will be listed.

Adverse events leading to intervention/study discontinuation

AE leading to intervention or study discontinuation will be listed.

Analysis of adverse events of special interest (AESIs)

AESIs will be selected for analyses as indicated in [Table 5](#). Number (%) of participants experiencing at least one event will be provided for each event of interest, by PT if applicable. Tables will be sorted as indicated in [Table 3](#).

Table 5 - Selections for AESIs

AESIs	Selection
Increase in alanine transaminase (ALT)	e-CRF specific tick box on the AE page
Pregnancy	Specific page
Symptomatic overdose (serious or nonserious) with IMP	Specific page

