9.4.4.2 Analyses of adverse events

Product Name: PRN473 (SAR444727)

Adverse events will be coded using the Medical Dictionary for Regulatory Activities (MedDRA; version in use by the Sponsor at the time of database lock). Clinical judgment should be used to determine the severity of AEs.

Adverse events will be classified into predefined standard categories according to chronological criteria:

- Pre-treatment AEs: AEs that occurred, worsened, or became serious during the pre-treatment period.
- Treatment-emergent AEs: AEs that occurred, worsened, or became serious during the TE period.
- Post-treatment AEs: AEs that occurred, worsened, or became serious during the post-treatment period.

If the onset date (or time) of an AE (occurrence, worsening, or becoming serious) is incomplete or missing, the AE will be considered as a TEAE unless a partial date (or time) shows it as a pre- or post-treatment event.

All AEs reported in the study will be listed, sorted by patient, onset date, and time.

Main summary will be per study period (Blinded Period, Open-Label Period) and overall.

If selected TEAEs from the Blinded Period can be clearly assigned to one of the study intervention treated lesions, they may be presented additionally assigned to the treatment of the corresponding lesion.

Any TEAEs which may occur between the first administration of placebo and the first administration of PRN473 Gel, 5% will be presented separately.

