1 INTRODUCTION

1.1 STUDY DESIGN

PRN473 is also known as SAR444727 and both terminologies are used in an interchangeable way in this document. For the reporting “SAR444727” will be used.

Study ACT17131 is a Phase 2a that consists of a randomized, double-blind, intra-patient placebo-controlled treatment period and an open-label uncontrolled treatment period.

The objective of the study is to evaluate the safety, tolerability, pharmacokinetics (PK) and preliminary efficacy of topically administered SAR444727 in up to 40 participants with mild to moderate atopic dermatitis (AD).

On Day 1 (Baseline) of the Blinded Period, 2 target lesions of 100 cm² area each with a difference no greater than 1 point in lesional Total Sign Score (TSS) are randomly assigned to treatment in an intra-participant 1:1 manner, with one lesion assigned to SAR444727 Gel 5% and the other to matching placebo (ie, same inactive ingredients). SAR444727 Gel 5% and matching placebo (ie, same inactive ingredients) are applied twice a day (BID, morning and evening) at a quantity of 2.5 mg/cm² to a 100 cm² area of each target lesion on Days 1-14 (Blinded Period). On Days 15-42 (Open-Label Period), participants are instructed to apply SAR444727 Gel, 5% BID to all AD-affected areas in a thin layer (excluding the scalp, palms, soles and genitals), and should continue to treat the assigned areas throughout the Open-label Period.

Participation will take approximately 13 weeks, including up to a 5-week screening period, a 6-week treatment period (2-week blinded and 4-week open label), end of study assessments 1 day after last dose, and a safety follow-up phone call 2 weeks after last dose.

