1.2 OBJECTIVE AND ENDPOINTS

Table 1 - Objectives and endpoints

Objectives	Endpoints
Primary	
Safety: To assess the safety and tolerability of PRN473 Gel, 5% versus placebo administered BID up to 6 weeks in participants with mild to moderate AD	Safety: 
Incidence and severity of AEsChanges in vital signs, ECGs, and laboratory testsAssessment of local cutaneous tolerability: incidence and severity of application-site events such as burning/stinging, itching, and erythema
PK: To evaluate the plasma PK of PRN473 following administration of multiple topical doses of PRN473 Gel, 5% for 42 days in participants with mild to moderate AD	
PK: Plasma PRN473 concentrations at specified timepoints

Objectives	Endpoints

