3.2.1 Definition of endpoint(s)

The primary endpoints are incidence and severity of the adverse events (AEs) defined in [Section 3.6.2](#), the standard clinical parameters (vital signs and electrocardiograms [ECGs]), the laboratory parameters defined in [Section 3.6.3.1](#) and the assessment of local cutaneous tolerability defined in [Section 3.6.3.2](#).

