3.6.3.2 Local cutaneous tolerability

The local cutaneous tolerability is assessed by the incidence and severity (grade) of application-site events such as burning/stinging, itching, and erythema.

Grading of application site local tolerability symptoms will be recorded using the grading scale (cf Protocol Appendix 4, Section 10.4.1) following each dosing during the blinded period. During the Open Label period symptom grading will record worst symptom observed on the lesional areas treated within approximately 30 min after dosing.

For each lesion, number and proportion of participants with at least one application-site event (such as burning/stinging, itching, and erythema) over the 2-week double-blind period, the 4-week Open label period, overall and by type of sign will be summarized. For each lesion, and by type of sign, the distribution of corresponding worst grade (intensity) will be summarized. The localization of the lesion on the body with an application-site event of local untolerability will be reported.

Burning/stinging sub-score assessments over time by lesion during blinded period and overall during Open-label period will be also summarized.

Overview of AEs linked to local cutaneous tolerability will be presented by SOC, PT for each study period and overall.

No analysis of the total score will be performed.

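### Coded adverse events at the target lesions have no guaranteed active-versus-placebo table: assignment to a lesion's treatment is optional and limited to undefined selected events

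*SAP*

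**What the plan says.** The primary objective in SAP 1.2 is "To assess the safety and tolerability of PRN473 Gel, 5% versus placebo administered BID up to 6 weeks". Adverse event incidence and severity is one of its endpoints, and local cutaneous tolerability is another. SAP 1.1 describes a within-participant allocation, "with one lesion assigned to SAR444727 Gel 5% and the other to matching placebo", with both products applied over the same 14 days.

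For coded adverse events, SAP 3.6.2 states: "Main summary will be per study period (Blinded Period, Open-Label Period) and overall". It then adds: "If selected TEAEs from the Blinded Period can be clearly assigned to one of the study interventions treated lesions, they may be presented". The matching sentence in Protocol 9.4.4.2 ends: "they may be presented additionally assigned to the treatment of the corresponding lesion". For adverse events connected with local tolerability, SAP 3.6.3.2 states: "Overview of AEs linked to local cutaneous tolerability will be presented by SOC, PT for each study period and overall".

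The graded signs are handled differently. Protocol 9.4.4.3 commits to summarising burning/stinging, itching and erythema by treatment in the Blinded Period. SAP 3.6.3.2 commits to counts, proportions and worst grades for each lesion.

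**The concern.** In a split-lesion design, the adverse events that can be compared with placebo are those located at a target lesion while the two lesions receive different products. Systemic events cannot be split, whatever the wording. For lesion-located events the plan makes the comparison discretionary in three ways: the events must be *selected*, the assignment must be clear, and the display *may* be made. None of the three is defined.

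Two things are at stake. A lesion-located reaction that is not a graded sign, or that appears between doses, could be reported without showing whether it arose under active gel or vehicle. Or the split could be shown for some events and not others, with nothing to show that the choice was made blind. The comparison matters here: Protocol 2.2.1.3 says that the gel may be a contact sensitiser, and Protocol Table 4 shows that active and placebo share most excipients. Separating drug from vehicle effects is what the placebo lesion is for.

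**Working it through.** The plan gives no event count, margin or power figure on this point, so there is nothing to reproduce. The check sets the sections side by side and then gives an illustration.

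**Which displays are committed, and by what grouping**

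- SAP 3.2.2, 3.6 and 3.6.2, and Protocol Table 8 and 9.4.4.2: coded events per participant, by period and overall. Every participant receives both products in the Blinded Period, so this grouping yields no placebo column.
- SAP 3.6.3.2, overview of events linked to local tolerability: by period and overall.
- Protocol 9.4.4.3 and SAP 3.6.3.2, graded signs: by treatment and per lesion. This is firm.
- SAP 3.6.2 and Protocol 9.4.4.2, coded events by lesion treatment: optional and selective.

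**Does other text supply a placebo column?**

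- SAP 3.1 sets analysis by intervention group as the default unless otherwise specified. Sections 3.6 and 3.6.2 specify otherwise for adverse events.
- The text before SAP Table 4 sorts tables on the experimental drug group, which hints at a group column. Table 3 footnote a sorts on overall incidence. The two conflict, and neither commits to a column.
- Protocol 9.4.4.2 separately presents events between the first placebo and the first active application on Day 1. That interval is not a comparison over the Blinded Period.

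**What the graded signs leave out**

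The scale in Protocol 10.4.1 covers burning/stinging, pruritus and erythema only. Protocol 8.2.6 has each lesion graded within about 30 minutes of dosing. Lesion-located events of another kind, or arising later, reach the report only as coded adverse events.

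**When selection can happen**

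The SAP is approved before database lock or the first interim but contains no selection rule. SAP 3.8.1 applies its conventions at the interim, when the biostatistician and programmer hold unblinded individual data. Nothing places the selection before that moment.

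**Illustration (assumed counts)**

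Take N = 40, the planned maximum. Suppose k participants each have one lesion-located event on one lesion, outside the graded signs. Let a be the number on the active lesion and k - a the number on placebo.

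- Period table: k/N. With k = 8, 8/40 = 20%, whatever a is.
- Active minus placebo: (2a - k)/N.
  - a = 8: 8/40 = +20 points.
  - a = 6: 15% - 5% = +10 points.
  - a = 0: -8/40 = -20 points.
- The range is always ±k/N. With half as many events, k = 4, it is ±10 points.

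Now suppose the true split is 6 active and 2 placebo, and any subset may be displayed. The displayed difference can run from (6 - 0)/40 = +15 to (0 - 2)/40 = -5 points, against a true +10.

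**The case against.** The strongest reply is that the application-site events named in the primary endpoint already have a firm placebo comparison, graded after every blinded-period dose. This stands. A reader might infer that the primary objective has no placebo comparison at all, and the documents do not support that. For the three graded signs, the by-treatment table also removes the ambiguity in the illustration. SAP 3.6.3.2 introduces these signs with a *such as*, which could be read more widely, but the grading scale has no other item.

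Second, the lesion display is additional. All treatment-emergent events are tabulated by period, and Protocol 9.4.4.2 lists every adverse event. So a reader should not infer that events could be hidden. However, no lesion field is promised in that listing, and a listing is not a pre-specified comparison.

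Third, a reader might infer that the sponsor plans to choose events after unblinding. No section says so. Causality is judged by an investigator who is blinded during the Blinded Period, and Protocol 9.5 foresees a dedicated interim analysis plan that is not among the documents and might hold a rule. What stands is that neither document available closes off a late choice.

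Fourth, SAP 3.6.2 has a fixed causality rule: a related event counts as related to active unless documented as related to the placebo lesion's formulation and not the active one. That rule governs relatedness, not a tabulation by lesion. It does suggest that lesion-level information can be recorded.

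Finally, the analysis is descriptive, in a signal-seeking study of up to 40. This limits the consequence but does not remove the value of a fixed display rule.

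**Conclusion.** The point holds in a limited form. Coded adverse events located at a target lesion, outside the three graded signs or the post-dose grading window, have no guaranteed comparison with placebo. The one display that would give it is open to selection after treatment codes are known. The exposure is selective attribution within the adverse event endpoint.

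Its size cannot be stated from the documents, which give no expected event count. On the assumed 8 of 40, the committed period table is compatible with any difference from -20 to +20 percentage points. That range assumes one event on one lesion per affected participant and no other by-lesion table covering those events. It shrinks in proportion to the number of such events.

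**What to change.** In SAP 3.6.2, and in the adverse event overview in 3.6.3.2, replace the optional wording with a fixed rule. All Blinded Period treatment-emergent events located at a target-lesion application area will be tabulated by preferred term and maximum intensity according to that lesion's treatment. The table shows participants with an event on the active lesion only, the placebo lesion only, or both. Events that cannot be assigned are shown separately.

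State that blinded staff record the lesion (one, the other, both, neither, or not assignable) before any treatment code is released, including for the interim. Align Protocol 9.4.4.2 at the next amendment, or record the change in SAP 3.9. Reconcile the two sorting rules (Table 3 footnote a and the text before Table 4).

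The cost is revised SAP wording, one extra table, and possibly one field on the adverse event page if the lesion is not already captured. No visit or procedure is added.

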3.6.3 Additional safety assessments

3.6.3.1 Vital signs, electrocardiograms (ECGs) and laboratory variables

The following variables will be analyzed. They will be converted into standard international units.

- Vital signs (see Section 8.2.2 of the protocol): heart rate, systolic and diastolic blood pressure, weight, temperature
- ECG variables (see Section 8.2.3 of the protocol): heart rate, PR, QRS, QT, and corrected QTc (according to Bazett/Fridericia)
- Laboratory variables (see Section 8.2.4.1 of the protocol): hematology, clinical chemistry, coagulation, urinalysis

For laboratory parameters, out-of-normal range definitions will be listed.

Data below the Lower Limit Of Quantitation/detection limit (LLOQ) will be replaced by half of the LLOQ, data above the Upper Limit Of Quantification (ULOQ) will be replaced by ULOQ value.

Quantitative analyses

When relevant, vital signs, ECG variables above and for laboratory variables, descriptive statistics for results and changes from Baseline as appropriate will be provided for each planned visit and time/analysis window.

For vital signs, ECG and laboratory variables, mean changes from Baseline with the corresponding standard error deviation will be plotted over time.

Analyses according to PCSA

PCSA analyses will be performed based on the PCSA list currently in effect at Sanofi at the time of the database lock. For laboratory parameters for which no PCSA criteria are defined, similar analyses will be done using out-of-normal ranges, if applicable. For parameters defined as efficacy/pharmacodynamic endpoints, PCSA summaries will not be provided.

Analyses according to PCSA will be performed based on the worst value during the TE period, using all measurements (either local or central, either scheduled, nonscheduled or repeated).

For laboratory variables above, the incidence of participants with at least one PCSA during the TE period will be summarized regardless of the baseline level and according to the following baseline status categories:

- Normal/missing
- Abnormal according to PCSA criterion or criteria

Summary statistics (including number, mean, median, Q1, Q3, standard deviation, minimum and maximum) of all ECG variables (raw values and changes from Baseline) will be calculated for each planned visit by intervention group. In addition, mean changes from Baseline with the corresponding standard errors will be plotted over time in each intervention group.

For ECGs, the incidence of participants with at least one abnormal ECG during the TE period will be summarized regardless of the baseline level and according to the following Baseline status categories:

- Normal/missing
- Abnormal

Listing of participants with QTc >480 msec and/or change from baseline QTc >60 msec

If any, an intext listing of participants with QTc >480 msec and/or change from Baseline QTc >60 msec will be provided.

3.6.3.2 Local cutaneous tolerability

The local cutaneous tolerability is assessed by the incidence and severity (grade) of application-site events such as burning/stinging, itching, and erythema.

Grading of application site local tolerability symptoms will be recorded using the grading scale (cf Protocol Appendix 4, Section 10.4.1) following each dosing during the blinded period. During the Open Label period symptom grading will record worst symptom observed on the lesional areas treated within approximately 30 min after dosing.

For each lesion, number and proportion of participants with at least one application-site event (such as burning/stinging, itching, and erythema) over the 2-week double-blind period, the 4-week Open label period, overall and by type of sign will be summarized. For each lesion, and by type of sign, the distribution of corresponding worst grade (intensity) will be summarized. The localization of the lesion on the body with an application-site event of local untolerability will be reported.

Burning/stinging sub-score assessments over time by lesion during blinded period and overall during Open-label period will be also summarized.

Overview of AEs linked to local cutaneous tolerability will be presented by SOC, PT for each study period and overall.

No analysis of the total score will be performed.

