9.2 SAMPLE SIZE DETERMINATION

No sample size calculations were performed due to the exploratory nature of this study.

The sample size of up to 40 for this study with patients receiving both PRN473 Gel, 5% and placebo is based upon empirical clinical consideration. The sample size is considered adequate to evaluate the safety, tolerability, and PK of topically administered PRN473.

This study is signal seeking and neither aimed nor powered to provide formal inferential statistical analyses.

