9.4.4 Analysis of safety data

The safety evaluation will be based upon the review of the individual values (clinically significant abnormalities), descriptive statistics (summary tables, figures) and, if needed, on statistical analysis (appropriate estimations, confidence intervals). No statistical significance tests will be performed on safety data.

Potentially clinically significant abnormality (PCSA) values are defined as abnormal values considered medically important by the Sponsor, according to predefined criteria/thresholds based on literature reviews and defined by the Sponsor for clinical laboratory tests, vital signs, and ECG parameters.

All the safety analyses will be performed based on the safety population. Where appropriate, supplemental analyses will be presented excluding observations after administration of rescue medication.

For all safety data variables, the following observation periods are defined and used for classification of AEs, determination of on-treatment PCSA values, and the last on-treatment value for laboratory and vital sign parameters:

- The pre-treatment period is defined as the time between informed consent signature and the first study intervention administration.
- The treatment-emergent period is defined as the time from the first study intervention administration through the End of Study visit.
- The post treatment period is defined as the time starting after the treatment-emergent period.

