9.4.4.3 Local cutaneous tolerability

Signs of local cutaneous intolerability as incidence and severity of application-site burning/stinging, itching, and erythema will be summarized for the Blinded Period by treatment (PRN473 Gel, 5% or placebo) and overall for the open-label phase.

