3.2.2 Main analytical approach

All the safety analyses will be performed based on the safety population defined in [Table 2](#).

The safety evaluation will be based upon the review of the individual values (clinically significant abnormalities), descriptive statistics (summary tables and figures). No statistical significance tests will be performed on safety data. No imputation will be performed.

Safety measures include AEs, Treatment-Emergent AEs (TEAEs), Serious AEs (SAEs), AEs leading to study intervention, treatment discontinuation (permanent or not), study discontinuation, and death. Overall AEs, TEAEs, and SAEs incidence tables will be presented by System Organ Class (SOC), high level group term (HLGT), high level term (HLT), and preferred term (PT for each study period and overall, showing the number (n) and percentage (%) of participants experiencing an AE. They will be described according to maximum intensity and relation to the study intervention.

Proportion of participants with at least 1 TEAE, treatment emergent SAE, TEAE leading to death, and TEAE leading to definitive treatment discontinuation will be tabulated by study period and overall.

For the changes in vital signs, ECGs and laboratory tests, the incidence of potentially clinically significant abnormalities (PCSAs) occurring during the TE period will be summarized overall and by baseline status.

For analysis local cutaneous tolerability see [Section 3.6.3.2](#).

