4 SAMPLE SIZE DETERMINATION

No sample size calculations were performed due to the exploratory nature of this study.

The sample size of up to 40 for this study with participants receiving both SAR444727Gel, 5% and placebo is based upon empirical clinical consideration. The sample size is considered adequate to evaluate the safety, tolerability, and PK of topically administered SAR444727.

This study is signal seeking and neither aimed nor powered to provide formal inferential statistical analyses.

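### Local tolerability against placebo is summarised lesion by lesion only, so the discordant pairs and the paired precision of the active–placebo difference cannot be recovered

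*SAP*

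**What the plan says.** The primary objective in SAP 1.2 (and Protocol section 3) is comparative: "To assess the safety and tolerability of PRN473 Gel, 5% versus placebo administered BID up to 6 weeks". Local cutaneous tolerability is one of the named primary endpoints. Two target lesions per participant are "randomly assigned to treatment in an intra-participant 1:1 manner" (SAP 1.1), and Protocol 8.2.6 has each target lesion graded after every dose in the Blinded Period.

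For the analysis, Protocol 9.4.4.3 says that application-site signs "will be summarized for the Blinded Period by treatment (PRN473 Gel, 5% or placebo) and overall for the open-label phase". SAP 3.6.3.2 plans, "For each lesion, number and proportion of participants with at least one application-site event (such as burning/stinging, itching, and erythema", and then the worst-grade distribution per lesion and sign, burning/stinging over time by lesion, the body location of lesions with events, and an overview of related adverse events. It specifies no active-by-placebo cross-table, discordant count, difference or interval.

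On safety in general, Protocol 9.4.4 bases the evaluation on individual values, descriptive statistics and, "if needed, on statistical analysis (appropriate estimations, confidence intervals". SAP 3.2.2 keeps the first two, does not mention the third, and states "No statistical significance tests will be performed on safety data". SAP 3.4, by contrast, gives exploratory lesional TSS, v-IGA-AD and PP-NRS active–placebo contrasts with 95% intervals.

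**The concern.** The blinded tolerability data are matched pairs: an outcome on the active lesion and one on the placebo lesion of the same person. Two marginal percentages do not describe such data fully. The same margins fit a trial in which every discordant participant reacted only under active, and one in which a sizeable minority reacted only under placebo. A reader would weigh these very differently when judging whether the drug, and not its vehicle or the participant's own skin, causes the reaction.

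This matters most where the margins are read with few pairs. SAP 3.8 plans an interim look at about 25 participants that may end the study on unfavourable signals, and SAP 3.8.1 applies the SAP's methods there as applicable.

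**Working it through.** **Stated figures.** There is none to reproduce. Protocol 9.2 says "No sample size calculations were performed due to the exploratory nature of this study", and SAP section 4 says "The sample size of up to 40 for this study with participants receiving both SAR444727Gel, 5% and placebo is based upon empirical clinical consideration". Neither document gives an event rate, so the counts below are assumptions; only n = 40 comes from the plan.

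**Notation.** Of n participants, b react only on the active lesion, c only on the placebo lesion, and a on both.

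**Step 1: the point difference.** (a + b)/n - (a + c)/n = (b - c)/n. It depends on the margins alone. With 12/40 and 8/40 it is 30% - 20% = 10.0 points, whatever the overlap a.

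**Step 2: its precision.** The simple paired standard error is sqrt[(b + c) - (b - c)²/n]/n, which depends on b + c and so on a.
- a = 8, so b:c = 4:0: sqrt(4 - 16/40)/40 = 4.7 points.
- a = 2, so b:c = 10:6: sqrt(16 - 16/40)/40 = 9.9 points.
- Treating the lesions as independent: sqrt(0.3×0.7/40 + 0.2×0.8/40) = 9.6 points in both cases.

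**Step 3: matched-pair score (Tango) intervals.** The limits solve (b - c - nD)/sqrt{n[2q + D(1 - D)]} = ±z. Here q = [sqrt(B² - 4AC) - B]/(2A), A = 2n, B = -b - c + (2n - b + c)D and C = -cD(1 - D).

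Check of the two lower 95% limits:
- 4:0 at D = 0.004: B = -3.696, C = 0, q = 0.0462. The statistic is 3.84/sqrt(3.855) = 1.96.
- 10:6 at D = -0.100: B = -23.6, C = 0.66, q = 0.2637. The statistic is 8/sqrt(16.70) = 1.96.

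| Split b:c | React on both | Difference | 95% interval | 80% interval |
|---|---|---|---|---|
| 4:0 | 8 | 10.0 | 0.4 to 23.1 | 5.4 to 17.7 |
| 10:6 | 2 | 10.0 | -10.0 to 29.4 | -2.9 to 22.7 |

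From the margins alone, the independent-samples Newcombe interval is -9.0 to 28.1 in both rows. The Wilson limits are 18.1 to 45.4% and 10.5 to 34.8%, so the lower limit is 10 - sqrt(11.9² + 14.8²) and the upper 10 + sqrt(15.4² + 9.5²).

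**Step 4: other assumed margins.** With 12/40 and 6/40 the difference is 15.0 points. The paired standard error runs from 5.6 points (all six placebo reactors also react on active) to 10.3 points (no overlap), against 9.2 unpaired. At 25 pairs with 8 and 4 events, the difference is 16 points and the paired standard error 7.3 to 13.5, against 11.9 unpaired.

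**The case against.** The strongest reply is that the plan is descriptive by declaration. No hypotheses are tested, both documents call the study signal seeking and unpowered for formal inference, and safety is to be read from individual values and summaries. That stands, and it is why this is an improvement and not an error. It does not argue against the fix: a cross-table is itself descriptive, an estimation interval is not a test, and the SAP already uses 95% and 80% intervals descriptively for exploratory efficacy.

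Four stronger readings are tempting, and the documents do not support them.
- A reader might infer that the trial cannot estimate how much worse active is tolerated than vehicle. It can: Step 1 shows that the difference follows from the planned margins.
- A reader might infer that the paired design goes unused. That is true of tolerability only; the mixed model for lesional TSS takes the participant as subject with an unstructured covariance across visit and treatment.
- A reader might infer that tolerability is the only primary endpoint with a placebo comparator. SAP 3.6.2 lets selected Blinded Period adverse events be shown by lesion treatment, though only optionally.
- A reader might infer that the SAP withdrew a promised safety interval. The protocol's allowance was conditional, the SAP is silent on safety intervals, and SAP 3.9 records no change.

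The illustration also deserves caution. The 4:0 split is complete overlap. The 10:6 split has two participants reacting on both lesions, slightly below the 40 × 0.30 × 0.20 = 2.4 expected if lesions reacted independently. The two rows show how wide the range can be, not what is likely.

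**Conclusion.** The concern holds in a limited form. For the one primary component firmly shown by lesion or treatment, under a placebo-comparative objective, the planned tables give the point difference but neither the discordant counts nor the paired precision, and these cannot be reconstructed afterwards from the margins. In the main illustration the standard error roughly doubles, from 4.7 to 9.9 points, and the lower 95% limit moves from 0.4 to -10.0, with no change in the planned incidence table. The worst-grade and over-time summaries do not fill the gap, because they too are marginal.

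The size rests on assumed event counts and on 40 complete pairs. That the margins do not determine the paired precision does not depend on those counts, except in trivial cases such as no events on one lesion type. No stated figure is wrong.

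**What to change.** In SAP 3.6.3.2, for the Blinded Period:

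1. State that the per-lesion summaries are by lesion treatment, in line with Protocol 9.4.4.3.
2. For any application-site event and for each sign, add a cross-table of each participant's worst grade, active lesion by placebo lesion, with the discordant counts shown.
3. For the same outcomes, add the paired difference in proportions with a matched-pair score interval, labelled descriptive and with no test, so that it agrees with SAP 3.2.2. Name one method, Tango or paired Newcombe, in advance.

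The cost is SAP wording and a few extra tables from grades already collected. Some tables will be sparse, and the intervals must not be read as tests. The Open-Label Period needs no such contrast, because all treated lesions then receive the active gel.
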